5.7 Withdrawal of Subjects

Subjects can withdraw from the study at any time. Reason for withdrawal will be recorded. Subjects may also be withdrawn from the study by LSIs and in agreement with the study PI for any of the following reasons: 1. New or worsening medical conditions (e.g., cancer, renal disease, end-stage cardiopulmonary disease, post-traumatic stress disorder, uncontrolled diabetes, etc.) that may interfere with study procedures or otherwise pose concern for subject health or safety, 2. New pregnancy, 3. Inability of subjects to comply with study procedures, 4. Other reasons deemed important to subject safety or data quality raised by the DSMB, IRB, FDA, or any other regulatory body that has the authority to do so. If subjects are deemed no longer safe to take the investigational drug but otherwise are able to participate in the study outcomes for the remainder of the study, they are encouraged to do so.

Female study subjects of childbearing potential will be encouraged to use effective birth control methods during the study. Pregnancy testing in female subjects of childbearing potential will be conducted as part of safety laboratory studies at each study visit according to the study flowsheet. Should pregnancies occur during the study, those female subjects will be withdrawn from the study. Information will be collected as to the pregnancy course, outcome and health of the newborn infant. Because LA is available as an over the counter supplement, male subjects whose female partners become pregnant will continue in the study, however pregnancy and birth outcomes of the female partners will be recorded and presented to the DSMB.

If a subject wants to withdraw from the study, the subject will contact the site study staff using the contact information and procedures on the ICF and request withdrawal. If a subject withdraws or is removed from the study for any reason and is unable or unsuitable to continue the study procedures off investigational drug, the reason and date of discontinuation of the investigational drug is recorded. At the time of study discontinuation, every effort will be made to schedule the subject for an early termination visit following the procedures for M24 without the MRI or Fall Count Diary if termination is within 6 months of the baseline visit, and M24 procedures with MRI but without fall count if termination is greater than 6 months of the baseline visit. Subjects withdrawn due to reportable adverse events and subjects with adverse events thought related to the study that are ongoing at the final study visit are followed for 30 days or until resolved, whichever is first, or longer per request of the Medical Monitor.

6.0 **Reporting:** All SAE, UAP, and PD are reported to the IRB within defined timelines.

6.1 Adverse event reporting

Adverse event (AE) information will be monitored in detail throughout the course of the study. AEs are defined as and will be graded as to their expectedness and attribution (unrelated, possibly, probably, or definitely related to the protocol). [name] will act as the medical monitor to determine relationship of AEs to the study intervention if uncertain. AEs will be reviewed by site treating neurologists, graded, and reported to the DCC. The DCC will code the events using MedDRA and will assist the CCC with IRB reporting per reporting guidelines.

6.2 Limited collection of non-serious AE

Some AEs are expected, so a limited set of AEs will be collected for this trial. Upper respiratory and urinary tract infections will not be tracked or reported, unless they reach an intensity of *severe*. Gastrointestinal distress is a known side effect of LA. Therefore only GI distress related and probably related to study of any intensity is tracked and reported. All other AEs are collected and stored at the study sites.

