SPMS participants using intention-totreat analysis. [name] et al conducted a single-center, 2-year randomized, double-blind, placebo-controlled phase 2 trial (n=51) of daily oral LA in SPMS (18). The LA cohort demonstrated a 68% reduction in the annualized rate of whole brain atrophy (0.21% vs -0.65%, p = 0.002, Fig 4). Although not powered to detect clinical outcomes, the LA cohort had a trend toward improvement in walking speed in the T25FW (-0.54 SD 0.36 vs 0.14 SD 0.25, p = 0.06). Overall LA was safe and well tolerated with high compliance and at the time, no unexpected deleterious adverse events (AE) were attributed to LA. A later review of AE's in light of safety data emerging from the present study indicate that the serious

adverse event of biopsy-proven glomerulonephritis and a second case of proteinuria in subjects in the LA cohort was related to lipoic acid (see above). To date, all three cases resolved within a 3-12 month period. Gastrointestinal (GI) upset was significantly greater in the LA cohort compared to placebo (17% v 3% p = 0.004). Unexpectedly, the LA cohort had a significantly lower number of falls than the placebo cohort (15% v 38%, p = 0.03). The results of this study formed the basis of the current research trial.

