5.1d.Unscheduled visits for relapse evaluation and adverse events (AE): Unscheduled visits will occur in the event of MS clinical relapses or investigations of AE of at least moderate severity *considered directly related to the study drug or study procedures*. The unscheduled visit for AE is for the purpose of evaluation by the treating neurologist, documentation, and reporting according to IRB guidelines. If sufficient medical documentation by other health providers for the symptoms of the AE exist, or if the symptoms had resolved by the time of reporting, the treating neurologist may use the medical documentation or telephone interview in lieu of an unscheduled visit. Asymptomatic elevations or depression in laboratory values considered related to the investigational drug do not require an unscheduled visit but instead follow the monitoring procedure (5.1m. Protection from risks). If AEs warranting an unscheduled visit for AE and the scheduled study visit are completed. An unscheduled visit for AE evaluation includes collection of case report forms for:

AE evaluation documentation including event history

General medical exam

Vital signs

Concomitant medications

Safety laboratory measures (per treating neurologist discretion)

Adverse events monitoring

SBQ-R

A protocol-defined MS clinical relapse is defined as new or recurrent neurological symptoms, not associated with fever or infection, lasting for at least 24 hours, which is

followed by a period of stability or improvement. In addition, a protocol-defined relapse requires an increase in the EDSS Functional System corresponding to the symptom(s) of the relapse, or an increase in the overall EDSS secondary to a functional change related to symptoms(s) of the relapse. A relapse is not considered an adverse event. MS clinical relapses can occur in PMS and may be treated by the usual treating neurologist with standard courses of intravenous methylprednisolone or oral steroids of less than 2 weeks duration.

An unscheduled visit should be conducted within 1 week of a reported MS clinical relapse. The unscheduled visit for MS clinical relapse evaluation includes:

MS clinical relapse evaluation documentation including

General medical exam

Vital signs

Concomitant medications

EDSS examination (blinded)

Safety laboratory measures (per treating neurologist discretion)

Adverse events monitoring

SBQ-R

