5.1j. Randomization. The assignment of subjects to the treatment arms will be based on permuted block randomization defined by study site. The Central Research Pharmacy and SCC will oversee the randomization schedule. The Central Research Pharmacy will also maintain a master list of all study subjects in order to ship appropriate amounts of bulk study drug to the US site pharmacies for individual subject packaging and shipping.

5.1k. Compliance and medication reconciliation: Compliance with taking the investigational drug will be encouraged at each visit and between visits by telephone calls. Unused pills will be collected at each study visit and if necessary, by mail between visits. The study site research pharmacies will conduct medication reconciliation with returned pills and provide feedback to research staff to monitor if compliance is less than 75% or more than 125% of prescribed doses to encourage proper compliance.

5.11. Risks: Risks of the investigational drug, study procedures, and potential loss of confidentiality are reviewed with potential subjects during the informed consent process. Risks, reporting, responses to risks, and methods to minimize risks are further outlined in section 6.0, Reporting and 7.0, Privacy and Confidentiality. Briefly, risks of the

investigational drug are minimized by adverse event reporting safety and safety laboratory studies. Risks of study procedures are minimized by careful screening procedures and trained study personnel. Risks of loss of confidentiality are minimized by limiting collection of PHI, limiting access of PHI to the minimum necessary study staff, and use of secure data transfer methods.

Risks of LA: Oral LA can cause physical side effects including gastrointestinal (GI) intolerance, nausea and vomiting and rash. LA may cause liver, renal and urinary disorders. There is a possibility of developing proteinuria and/or membranous glomerulonephritis due to study drug. It is not known how LA could affect a fetus. LA may increase the risk of hypoglycemia in diabetics. The risks of LA taken with DMTs or with alcohol are unknown.

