Adverse and serious adverse events will be tabulated and compare the differences in the occurrence and the frequencies between the two groups. The frequency of side effects will be compared using χ^2 tests or Fisher's exact test as appropriate depending on the number of adverse events seen. For evaluation of patient safety, laboratory test results at baseline and changes from baseline will be summarized and compared using t-tests for continuous measures and Fisher's exact test for proportions.

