6.3 Limited reporting of AE

Not all AE captured at sites are reported to the DCC. The limited set of AE reported to the DCC via the REDCap database is according to guidelines in 6.3a below. Serious AE (SAE) and select UP and PD are reported under expedited guidelines according to IRB and other monitoring entity requirements.

AE Intensity*	AE relate study	d to	AE probably related to study	re	possibly lated to study	AE unrelated to study	
Mild	REDCa	p	AE Log only	AE log only		AE log only	
Moderate	REDCap		REDCap	AE log only		AE log only	
Severe	REDCa	ıp	REDCap	REDCap		REDCap	
SAE	REDCa	р	REDCap	REDCap		REDCap	
UP with risk to subjects or others	REDCa	p	REDCap	AE log only		AE log only	
Severe PD: REDCap		Moderate PD: REDCap		Cap. Mild PD: AE log only		E log only	

6.3a Limited reporting of AE, UP, and PD to the DCC. Bold items require expedited reporting to the DCC via REDCap.

* Increases after Screen in CTCAEv5 grades (ALT, AST), new ACR >300mg/g, and new eGFR<60 are always reported in REDCap regardless of intensity or relationship to study. GI distress related and probably related to study of any intensity is reported in REDCap.

ALT, Alanine Aminotransferase; AST, Aspartate Aminotransferase; ACR, Albumin to creatinine ratio

6.4 Adverse event (AE) definition: Any untoward or undesirable, although not necessarily unexpected, event experienced by a human subject that may be a result of:

- The interventions and interactions used in the research.
- The collection of identifiable private information in the research.
- An underlying disease, disorder, or condition of the subject.
- Other circumstances unrelated to the research or any underlying disease, disorder, or condition of the subject.

6.5 Serious Adverse Event (SAE) definition: Any AE that:

- Is fatal.
- Is life-threatening.
- Is persistent or significantly disabling or incapacitating.
- Results in inpatient hospitalization or prolongation of hospitalization.
- Results in psychological or emotional harm requiring treatment.
- Creates a persistent or significant disability.
- Causes a congenital anomaly or birth defect.
- Results in a significant medical incident (considered to be a serious study related event because, based upon appropriate medical judgment, it may jeopardize the subject and may require medical or surgical intervention to prevent one of the outcomes listed in this definition).

6.6 Unanticipated problem (UP) definition:

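### Mild and moderate urinary tract infections are kept out of every adverse event record, so their frequency cannot be compared by arm, and section 6.2 conflicts with sections 6.1 and 6.3a

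*Combined protocol and SAP*

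**What the plan says.** Section 6.2 limits collection of non-serious adverse events because some are anticipated: "Some AEs are expected, so a limited set of AEs will be collected for this trial". Its first restriction is "Upper respiratory and urinary tract infections will not be tracked or reported, unless they reach an intensity of" severe. After a separate rule for gastrointestinal distress, the section ends: "All other AEs are collected and stored at the study sites".

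Section 5.1l, on the risks of lipoic acid (LA), says "LA may cause liver, renal and urinary disorders" and goes on to name proteinuria and membranous glomerulonephritis.

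Section 6.1 has treating neurologists review and grade adverse events and report them to the data coordinating center, with no exception for UTI. The 6.3a table assigns a destination by intensity and relatedness, and its footnote has no infection exception either. Section 5.6b plans the comparison by arm: "The frequency of side effects will be compared using χ^2 tests or Fisher's exact test as appropriate". Under section 6.8 the DSMB receives quarterly aggregate reports grouped by arm, limited to what section 6.3 lets through.

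**The concern.** In section 6.2 the final sentence covers only the other events. Mild and moderate UTIs therefore do not get even the site log entry that an unrelated mild event of another kind receives. For most events the plan filters what reaches the central database but keeps a retrievable site record. Here nothing is kept.

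That an event is anticipated is a weak reason not to record it in a randomized, blinded trial. Background events should fall about equally in the two arms, and an excess in one arm is what the comparison is there to show. The plan does not treat anticipation as a general reason to stop recording: gastrointestinal distress, a known effect of LA, is still reported at any intensity when judged related or probably related.

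At stake is the UTI line of the final safety table, in an organ system that the protocol lists as possibly affected. There is also a practical problem: a site that reads 6.2 and a site that reads 6.3a would handle the same event differently.

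**Working it through.** **Step 1. Where does a non-serious, non-severe UTI go?** The columns for 6.3a follow its table; the last column follows 6.2.

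| Intensity | Relatedness | 6.3a table | 6.2 |
|---|---|---|---|
| Mild | Related | REDCap | No record |
| Mild | Probably, possibly or unrelated | Site AE log | No record |
| Moderate | Related or probably related | REDCap | No record |
| Moderate | Possibly related or unrelated | Site AE log | No record |

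These rows cover eight combinations. The 6.3a table sends three to REDCap and five to the site log, and leaves none unrecorded. Section 6.2 leaves all eight unrecorded. The gastrointestinal rule of 6.2 is repeated in the 6.3a footnote, but the infection rule is not, so the table does not signal that 6.2 overrides it.

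**Step 2. What is still captured?**
- Severe UTIs (6.2 and 6.3a) and serious UTIs (6.3a; section 6.2 is headed as applying to non-serious events).
- Renal laboratory events: "new ACR >300mg/g, and new eGFR<60 are always reported in REDCap regardless of intensity or relationship to study". Urine protein is tested every 3 months (5.1m, 5.5e).
- Urinary adverse events that are not infections, which fall under the closing sentence of 6.2.
- An indirect trace of treated infections in the concomitant medication review (5.5d). That section does not say that the indication is recorded.

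The loss is therefore confined to non-severe, non-serious UTIs.

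**Step 3. Illustration of size.** The plan has no figure to reproduce here: the documents give no UTI rate, no severe fraction and no effect size. From the plan I take 59 per arm (5.6a). The rates below are assumptions. The test is two-sided at 5%, with the normal approximation

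power = Φ[(d − 1.96·se0)/se1], where d is the difference in proportions, se0 = √(2·p̄(1−p̄)/59), p̄ is the mean of the two proportions, and se1 = √((p1(1−p1) + p2(1−p2))/59).

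- All UTIs recorded, 20% vs 40%: p̄ = 0.30, se0 = 0.0844, se1 = 0.0823; (0.20 − 0.1654)/0.0823 = 0.42; power 66% (Fisher's exact test 60%).
- All UTIs recorded, 20% vs 30%: p̄ = 0.25, se0 = 0.0797, se1 = 0.0792; (0.10 − 0.1562)/0.0792 = −0.71; power 24%.
- Severe only, if one tenth of the first case reached severe, 2% vs 4%: power 9% (Fisher 1%).
- Severe only, with a larger assumed severe share, 5% vs 10%: power 18% (Fisher 9%).

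**Step 4. Number of extra records.** If the 25% who drop out (5.6a) leave on average at the midpoint, mean exposure is 0.75 × 1 + 0.25 × 0.5 = 0.875 of two years. Person-years = 118 × 2 × 0.875 = 206.5. At an assumed 0.2 to 0.5 UTIs per person-year, that is 206.5 × 0.2 ≈ 41 to 206.5 × 0.5 ≈ 103, so roughly 40 to 100 records for the whole trial.

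**The case against.** The strongest reply is that limiting collection of common events is a deliberate, stated choice, and that the renal risk the protocol spells out is proteinuria and membranous glomerulonephritis. That risk is covered closely by scheduled urine protein tests, mandatory REDCap reporting of the renal laboratory thresholds, and laboratory comparisons between arms. The documents do not name UTI as an effect of LA; counting it among urinary disorders is an inference. All of this stands, and it limits the point to one event type.

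A reader might infer that the trial is blind to any urinary signal. Step 2 shows that it is not. Three further arguments are tempting and should not be used:
- **The pilot's later safety review.** The Introduction says that pilot events were re-attributed "in light of safety data emerging from the present study", but those events were glomerulonephritis and proteinuria. A serious event or a new ACR above 300 mg/g would reach REDCap today.
- **The relapse definition.** It requires symptoms "not associated with fever or infection", but the unscheduled visit has its own examination, vital signs and discretionary laboratory tests, and does not depend on the adverse event log.
- **Urine protein.** The documents do not say that infection affects it, and the monitoring rules act on measured values.

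It is also fair to say that full recording may detect little: power is only about 24% for 20% versus 30%. That weakens any claim about lost power. It does not justify keeping no record, because safety tables are read descriptively as well as by test. Finally, one could argue that 6.2 is the specific rule and prevails over 6.1 and 6.3a. The documents do not say so, and the 6.3a footnote repeats one of the two exceptions in 6.2 but not the other.

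**Conclusion.** The point holds in a limited form. Followed as written, section 6.2 leaves non-severe, non-serious UTIs without any adverse event record, so their frequency cannot be compared by arm or re-examined later, although urinary disorders are listed as a possible effect of LA. Separately, 6.2 contradicts 6.1 and all eight mild and moderate cells of the 6.3a table.

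Both conclusions rest on the text alone. The power figures and record counts rest on assumed UTI rates and serve only to show scale. The point does not bear on the primary outcome or on renal laboratory monitoring, and it is not evidence that LA causes UTI. It is a modest, inexpensive improvement to safety data capture; events that go unrecorded may not be recoverable afterwards.

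**What to change.** - In 6.2, take UTIs out of the exclusion. Upper respiratory infections can stay excluded.
- Record UTIs of any intensity, with date, intensity and relatedness, at least on the site AE log. Adverse events are already reviewed at study visits and at the calls between visits, so no new contact is needed.
- In the final safety table, show by arm the number of subjects with at least one UTI. Because the trial was already running when this version was written, state the date from which recording applied.
- Reconcile 6.1, 6.2 and 6.3a so that each event has one destination. If any infection exception is kept, repeat it in the 6.3a footnote.

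The cost is a few sentences of protocol text, collation of site-log entries for the final table, and modest data entry: roughly 40 to 100 short records if the assumed 0.2 to 0.5 UTIs per person-year applied for the whole trial, and fewer if recording starts partway through.

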6.3 Limited reporting of AE

Not all AE captured at sites are reported to the DCC. The limited set of AE reported to the DCC via the REDCap database is according to guidelines in 6.3a below. Serious AE (SAE) and select UP and PD are reported under expedited guidelines according to IRB and other monitoring entity requirements.

AE Intensity*	AE relate study	d to	AE probably related to study	re	possibly lated to study	AE unrelated to study	
Mild	REDCa	p	AE Log only	AE log only		AE log only	
Moderate	REDCap		REDCap	AE log only		AE log only	
Severe	REDCa	ıp	REDCap	REDCap		REDCap	
SAE	REDCa	р	REDCap	REDCap		REDCap	
UP with risk to subjects or others	REDCa	p	REDCap	AE log only		AE log only	
Severe PD: REDCap		Moderate PD: REDCap		Cap. Mild PD: AE log only		E log only	

6.3a Limited reporting of AE, UP, and PD to the DCC. Bold items require expedited reporting to the DCC via REDCap.

* Increases after Screen in CTCAEv5 grades (ALT, AST), new ACR >300mg/g, and new eGFR<60 are always reported in REDCap regardless of intensity or relationship to study. GI distress related and probably related to study of any intensity is reported in REDCap.

ALT, Alanine Aminotransferase; AST, Aspartate Aminotransferase; ACR, Albumin to creatinine ratio

6.4 Adverse event (AE) definition: Any untoward or undesirable, although not necessarily unexpected, event experienced by a human subject that may be a result of:

- The interventions and interactions used in the research.
- The collection of identifiable private information in the research.
- An underlying disease, disorder, or condition of the subject.
- Other circumstances unrelated to the research or any underlying disease, disorder, or condition of the subject.

6.5 Serious Adverse Event (SAE) definition: Any AE that:

- Is fatal.
- Is life-threatening.
- Is persistent or significantly disabling or incapacitating.
- Results in inpatient hospitalization or prolongation of hospitalization.
- Results in psychological or emotional harm requiring treatment.
- Creates a persistent or significant disability.
- Causes a congenital anomaly or birth defect.
- Results in a significant medical incident (considered to be a serious study related event because, based upon appropriate medical judgment, it may jeopardize the subject and may require medical or surgical intervention to prevent one of the outcomes listed in this definition).

6.6 Unanticipated problem (UP) definition:

- Any event that is not expected given within the context of the study.
- Any event that places subjects or others at a greater risk of harm or discomfort relative to what was previously known.
- No harm to a subject needs to occur for an event to be an unanticipated problem.

6.7 Protocol Deviation (PD): The term "protocol deviation" is not defined by either the HHS human subjects regulations (45 CFR 46) or the FDA human subjects regulations (21 CFR 50). All PD are graded by the treating neurologist and entered into REDCap. Severe PD have expedited reporting to the DCC via REDCap. Moderate PD are entered into REDCap according to the usual timelines. Mild PD are recorded on the site AE log only.

6.7a. Mild PD:

- The deviation resulted in no harm or risk of harm to research participants; or
- The deviation did not result in or require any substantive action to be taken or result in a substantive change to the subject's condition or status (i.e., did not

affect the subject's participation in a substantive way, did not result in a change to the subject's emotional or clinical condition, did not cause an adverse experience or require a change to the clinical care of the subject, etc.)

- The deviation had no substantive effect on the value of the data collected (i.e., the deviation does not confound the scientific analysis of the results);
- The deviation did not result from willful or knowing misconduct on the part of the investigator(s);
- The deviation is easily corrected (e.g., consenting a subject with an old version of an ICF, recording data on an expired/incorrect form, forgetting to record data that may be acceptably recorded at the next visit, etc.)

6.7b. Moderate PD:

- The deviation resulted in a harm or risk of harm that is not significant; or
- The deviation resulted in the need for minimal risk interventions, such as those defined in 45CFR46.110 and 21CFR56.110;
- The deviation resulted in the loss or improper collection or recording of some data for one or more subjects, but did not invalidate the entire data set for the study;
- The deviation resulted in a regulatory violation that can be acceptably resolved;
- Repeated minor protocol deviations from the same laboratory, site or research team; or
- There has been a failure to follow action ordered to correct minor or moderate protocol deviations.

6.7c. Severe PD:

- The deviation resulted in or required a substantive action to be taken or resulted in a change to the subject's condition or status;
- The deviation has significantly harmed or posed a risk of significant harm to research participants;
- The deviation has substantially damaged the scientific integrity of the data collected for the entire study;
- The deviation is evidence of willful or knowing misconduct on the part of the investigator(s);
- The deviation involves serious or continuing noncompliance with federal, state, or local research regulations;
- There have been repeated minor and/or moderate protocol deviations from the same laboratory, site or research team;
- There has been a failure to follow action ordered to correct minor and/or moderate protocol deviations;

• There has been a failure to follow action ordered in accordance with the emergency action provision of this policy.

